6.2.3.2 Bleeding times

The bleeding time, as measured by the Simplate[®] R technique, will be read directly from the CRF. Bleeding times which are recorded as being greater than 60 minutes in the CRFs will be treated as being exactly 60 minutes in calculating the mean, but all summary statistics associated with that observation will be asterisked and identified with a footnote indicating that the summary statistics are biased.

6.3 Description of analysis sets

There are two populations in this study. All subjects randomized to treatment who receive at least one dose of study drug will be included in the safety population. This population will allocate subjects to the treatment actually received and not treatments randomized (although the two should concur). The per-protocol (PP) population is defined as a subset of the safety population, excluding those subjects with a protocol deviation felt to significantly influence either the pharmacokinetics or the pharmacodynamics of the drug. Definitions of all such protocol deviations will be made in the SAP. Examples include, but are not limited to, major changes in the administration of study drug or co-administration of medications expected to affect the pharmacokinetics or pharmacodynamics (however these are not all deviations excluded from PP population).

All safety data will be summarized using the safety population. Pharmacokinetic data will be summarized using the PP population excluding subjects who received placebo. Aggregometry and bleeding time data will be summarized using the PP population. In the case of the PP and safety populations being identical, only the safety population will be used throughout; this decision will be taken at the time of clean file and documented in the SAP.

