Study D5130C05239 evaluated the safety and tolerability of multiple ascending doses (tablets) of AZD6140 in healthy male and female subjects in Europe. Once and twice daily dosing regimens of AZD6140 with total daily doses ranging from 50 mg to 600 mg administered for 5 days at each dose level (a total duration of 15 or 20 days) were studied, compared with 75 mg clopidogrel. Multiple doses of AZD6140 were well tolerated. The pharmacokinetics (PK) of AZD6140 following multiple oral dosing was approximately linear over 50 mg to 600 mg. Maximum plasma concentrations (C_{max}) were reached within 2 to 4 hours after dose intake, and the mean terminal half-life ($t_{1/2}$) of AZD6140 ranged from 6 to 13 hours. The metabolite area under the plasma concentration-time curve (AUC) and C_{max} were about 35% of the corresponding parameters for AZD6140 and were approximately linear over 50 mg to 600 mg dosing of AZD6140. Greater than 80% inhibition of platelet aggregation was observed at all doses studied. In terms of inhibition of platelet aggregation, twice-daily doses were superior to the equivalent total daily dose given every 24 hours. All total daily doses of AZD6140 above 200 mg were superior to once-daily doses of 75 mg clopidogrel in terms of pharmacodynamics (PD) response. In addition, in this study, the effect of food on the PK and PD of AZD6140 was studied in an exploratory way (comparison between the data under fasting condition on Day 15 and under fed condition on Day 16). Plasma concentrations and AUC values of AZD6140 were slightly higher following administration of AZD6140 under fed condition. There did not appear to be any effect on those for the metabolite. Due to the study design, however, the exact magnitude of the effect of food could not be estimated from these data. There was no obvious effect of food on PD response.

No serious adverse events (SAE) were observed in the 11 Phase I studies completed to date. In 9 studies, which have been unblinded and/or reported, 233 healthy subjects were randomised, and 195 healthy subjects received at least 1 dose of AZD6140. Purpura, headache, dizziness, respiratory infection, tachycardia and lymphadenopathy were the most common adverse events reported in some of these trials. However, the causal relationship of these adverse events to AZD6140 is uncertain.

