3.4.5 Concomitant medication

Subjects should refrain from taking prescribed or over-the-counter medications including herbal remedies and vitamin preparations throughout the study unless approved by the sponsor and the investigator(s).

Any medication, which is considered necessary for the subject's safety and well-being, may be given at the discretion of the investigator(s). The administration of all medication (including investigational products) must be recorded in the appropriate sections of the CRF from 2 weeks prior to Visit 1.

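### The single per-protocol set excludes for a deviation affecting either PK or PD, so a deviation relevant only to platelet function also removes valid AUCss,τ and Css,max from the primary PK comparison

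*Supplement*

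**What the plan says.** Protocol section 6.3 limits the analysis sets to a safety set and one PP set: "There are two populations in this study". The PP set is the safety set "excluding those subjects with a protocol deviation felt to significantly influence either the pharmacokinetics or the pharmacodynamics of the drug". One of the examples it gives of an excluding deviation is "co-administration of medications expected to affect the pharmacokinetics or pharmacodynamics".

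The same set then serves both kinds of endpoint. For PK: "Pharmacokinetic data will be summarized using the PP population excluding subjects who received placebo". For PD: "Aggregometry and bleeding time data will be summarized using the PP population". Of the exclusion rule itself, only the list of deviations is deferred: "Definitions of all such protocol deviations will be made in the SAP". No SAP is among the documents.

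Section 6.4(b) names AUCss,τ and Css,max as the primary PK parameters and bases the conclusion of similar exposure on the 90% confidence intervals for their Japanese/Caucasian ratios. It does not name a population again, so the PP set applies through section 6.3. PK is a primary objective (section 2.1) and PD a secondary one (section 2.2).

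**The concern.** The exclusion rule joins PK and PD with an either/or and acts on whole subjects. A deviation that matters only for a secondary endpoint therefore takes a subject out of the primary PK comparison, although nothing is wrong with his concentrations.

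The case can arise. Section 3.4.5 lets the investigator give medication considered necessary for a subject's safety and well-being, and section 1.1 names headache among the more common events in some earlier trials. Appendix D itself warns that aspirin lengthens bleeding time in many people. That a single dose of such a drug leaves AZD6140 levels unchanged is an assumption of the example. The rule works the same way for any drug that acts on platelets alone.

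What is at stake is precision in the comparison of exposure between the ethnic groups. The sample size in section 6.5 leaves little margin at the planned number of evaluable subjects, and its 20% allowance is described as covering withdrawals, not PP exclusions.

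**Working it through.** **Inputs (section 6.5 unless noted).** 12 evaluable active subjects per arm, hence 2 × 12 = 24 per ethnic group pooled over the two doses; between-subject CV 38.1%; limits 0.70 to 1.43; true ratio 1; two one-sided t-tests at 5% on the log scale; 60 active subjects randomized, hence 30 per ethnic group. The number of PD-only exclusions is not in the documents. It is taken here as an assumption, 0 to 3 per group.

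**Formulas.**
- Log-scale SD: σ = √ln(1 + 0.381²) = 0.368.
- Standard error of the log ratio: SE = σ·√(1/n₁ + 1/n₂).
- Degrees of freedom: n₁ + n₂ − 3 (additive model with ethnic group and dose).
- Power: the probability that the estimate ± t₀.₉₅·SE, with estimated SE, lies within ln 0.70 = −0.357 to ln 1.43 = 0.358, by numerical integration over the distribution of the variance estimate.

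**The plan's own figures first.**
- Pooled, 24 v 24: SE = 0.368 × √(2/24) = 0.106, 45 df, power 90.4%. The plan says at least 90%; it reproduces.
- Per dose, 12 v 12, limits 0.50 to 2.00, 22 df: power 99.5%. The plan says at least 99%; it reproduces.
- Enrolment: 48/(1 − 0.20) = 60; it reproduces.

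**Effect of PD-only exclusions on the pooled comparison (one parameter).**

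| Evaluable per ethnic group | Situation | Power |
|---|---|---|
| 30 v 30 | all 60 active subjects evaluable | 96.1% |
| 28 v 28 | two lost per group from 30 | 94.7% |
| 24 v 24 | planned number; also six lost per group from 30 | 90.4% |
| 23 v 24 | one lost from the planned number | 89.65% |
| 22 v 24 | two lost, same group | 88.8% |
| 23 v 23 | one lost per group | 88.9% |
| 22 v 22 | two lost per group | 87.1% |
| 21 v 21 | three lost per group | 85.1% |

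Section 6.4(b) requires both AUCss,τ and Css,max to fall within the limits, so power for the joint conclusion cannot exceed these figures. With endpoint-specific sets, a PD-only deviation leaves the PK number, and so the power, unchanged.

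**Replacement.** Section 3.4.3 triggers replacement on the number of AZD6140 subjects expected to complete the study. A subject who completes and is later left out of the PP set still counts as a completer, so his loss does not trigger it.

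**The case against.** The strongest reply is that the working content is left to the SAP, and that exclusion is a judgement, not automatic. Both are true of which deviations count. But what section 6.3 defers is the definition of deviations affecting either PK or PD. It has already fixed a single set and its use for both endpoints. A SAP that kept a PD-only case in the PK comparison would have to depart from that text. This is therefore a stated rule with an unwanted result, not a missing detail.

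It is also fair to say that opportunities are few. Other medication is barred from two weeks before screening and restricted to follow-up (sections 3.3.3 and 3.3.4), subjects are resident from Day −2 to Day 13, and dosing is supervised (section 3.4.6). The figures below 90% arise only after the full 20% allowance has been used. All of this stands and keeps the expected effect small. A common population is also defensible for the PK/PD relationship, but an intersection set provides that without thinning the PK comparison.

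A reader might infer more than the documents support:
- **That the loss is biased.** Center and ethnic group coincide, so different prescribing could give unequal exclusions. Nothing in the documents says that prescribing differs or that exclusions would follow exposure, and section 1.1 calls the causal relation of the reported events to AZD6140 uncertain.
- **That data are thrown away.** Section 6.2.2 still has concentrations listed and plotted for all subjects who receive AZD6140. Only the PP summaries and the comparison omit the subject.
- **That the converse case harms the primary result.** A PK deviation on Day 9 properly removes the Day 10 parameters. What is needlessly lost is the earlier data in descriptive summaries.
- **That the sample size is wrong.** It reproduces.

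**Conclusion.** The point holds as a fault in the definition of the analysis set. Followed as written, section 6.3 removes valid values of the primary PK parameters for deviations that concern only platelet function.

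Its size depends on a count that the documents do not give and that is probably small. With full evaluability there is ample room: 96.1%, and still 90.4% after six exclusions per group. At the planned 24 per group there is almost none: one needless exclusion takes power just under 90%, and two per group take it to 87.1%.

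These figures assume CV 38.1%, a true ratio of 1, no interaction between dose and ethnic group, and one parameter at a time. The example further assumes that the co-medication does not alter AZD6140 concentrations. Bias between the centers is only a possibility. The change is worth making because it is nearly free, not because a large loss is expected.

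**What to change.** In section 6.3, replace the single PP population by two sets, and carry them into the SAP:

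- **PK-evaluable set:** active subjects, excluding only for deviations that affect concentrations of AZD6140 or AR-C124910XX. Name this set in section 6.4(b) for the ratio comparison.
- **PD-evaluable set:** excluding only for deviations that affect aggregation or bleeding time, including those that act through altered PK.
- **Affected period only:** apply each exclusion to the period that the deviation can have influenced, so that earlier data, such as the Day 1 profile before a later deviation, are kept.
- **PK/PD relationship:** analyze the intersection of the two sets.

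The cost is a few sentences and one more analysis-set flag, with no extra data or subjects. The PK and PD summaries may then rest on slightly different subjects, which the tables should state.

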3.1.2 Stopping criteria for dose escalation

Prior to dosing in Cohort B, the safety results up to 72 hours after the final dose of Visit 2 in Cohort A will be evaluated by the principal investigator and study team physician of AstraZeneca in each site. **In Japan**, written approval from the sponsor will be obtained before dose escalation. Adverse events and all the other safety related data, with particular attention to events that may be caused by increases in bleeding times, clinical safety labs, and clinically significant changes in ECGs will be reviewed for Cohort A. If it is anticipated that subjects may experience risk from further dose escalations, then the escalation to the next dose group may be stopped after discussions between the principal investigator and the sponsor's physician have taken place.

The dose escalation for Cohort B will be discontinued if any of the following tolerability or safety symptoms occur in at least three individuals who received AZD6140.

- AST and/or ALT increase ≥ 3 times upper limit of reference range at the study center for which the causality of AZD6140 can not be excluded
- Significant prolongation of the bleeding time (e.g. >30 minutes increase compared to baseline), as judged by the investigator, together with moderate to severe bleeding events and/or significant abnormalities of laboratory findings/vital signs, for which the causality of AZD6140 can not be excluded

The discontinuation of dose escalation will be considered if the following tolerability or safety symptoms occur in at least one subject.

- Severe and serious adverse events for which the causality of AZD6140 cannot be excluded

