3.1.3 Criteria for discharge

Prior to discharging subjects on Day 13 of Visit 2, the safety results up to 72 hours after the final dose will be evaluated by the principal investigator. The following will be evaluated:

- All complete and brief physical examination
- Laboratory tests
(If the results of the 24-hour post-final dose laboratory test (Day 11) shows a significant abnormality, as determined by the principal investigator, the test will be repeated at 48-hours post-final dose (Day 12). If these results show clinically significant abnormalities, the principal investigator will contact the sponsor's physician to discuss the appropriate course of action.)
- Pulse, BP, BT and ECG
- The presence and type/intensity of AE
- Bleeding times
(The principal investigator must assess bleeding time for every subject before discharge. In principal, the principal investigator must not discharge any subjects whose bleeding time is longer than 12 minutes. Bleeding time will be performed at 24-hour (Day 11) after final dosing of investigational product. If the bleeding time at 24-hour after final dosing is longer than 12 minutes, bleeding time will be repeated at 48-hours (Day 12) after final dosing. If the bleeding time at 48-hour after final dosing is shows longer than 12 minutes, the principal investigator will contact the sponsor's physician to discuss the appropriate course of action.)

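### Bleeding time is summarized only in the per-protocol set, so when that set is smaller than the safety set no table describes it in all dosed subjects

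*Supplement*

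**What the plan says.** Section 6.3 defines two populations. The safety population is everyone randomized who took at least one dose. The PP population is a subset of it, "excluding those subjects with a protocol deviation felt to significantly influence either the pharmacokinetics or the pharmacodynamics of the drug". The examples given are "major changes in the administration of study drug or co-administration of medications expected to affect the pharmacokinetics or pharmacodynamics"; the full definitions are left to the SAP, which is not among the documents.

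The assignments follow in the same section. For safety variables, "All safety data will be summarized using the safety population". For the two PD variables, "Aggregometry and bleeding time data will be summarized using the PP population". There is one exception: "In the case of the PP and safety populations being identical, only the safety population will be used throughout".

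Section 6.4(c) plans summaries, listings and graphs of bleeding time by treatment group and ethnic group. It names no second population.

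Elsewhere bleeding time has a safety role. Section 3.1.1 includes it in the safety review before multiple dosing. Section 3.1.2 says "The dose escalation for Cohort B will be discontinued if any of the following tolerability or safety symptoms occur in at least three individuals", and one of the two listed items begins "Significant prolongation of the bleeding time". Section 3.1.3 says that, as a general rule, "the principal investigator must not discharge any subjects whose bleeding time is longer than 12 minutes". Section 3.3.5.1 makes prolongation part of an individual discontinuation criterion.

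**The concern.** Safety and tolerability are a primary objective (section 2.1), and section 3.2 describes this as the first multiple-dose study in Japanese subjects. The drug inhibits platelet aggregation, so bleeding time bears directly on its expected risk. A reader of the study report will want to know how bleeding time behaved in everyone who was dosed.

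The PP set does not answer that question, and its exclusions are not neutral for this variable. A subject leaves the set because a deviation is thought to influence pharmacokinetics or pharmacodynamics, and bleeding time is a pharmacodynamic response. Exclusion is therefore tied to things expected to change the value being summarized. What is at stake is a descriptive table and its graphs. No hypothesis test, power figure or dosing decision depends on them.

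**Working it through.** The plan gives no figure for bleeding time to reproduce. Its only power calculation concerns the pharmacokinetic comparison between ethnic groups and does not bear on this point. The check is mainly a reading of the sections side by side.

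**Step 1: when a safety-set summary exists.** Under section 6.3 there are two cases.

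- PP and safety sets identical: the safety set is used for everything. Nobody is excluded and the issue does not arise.
- PP set smaller than the safety set: bleeding time is summarized in the PP set, and neither 6.3 nor 6.4(c) adds a second summary.

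So the safety-set summary is planned only in the case where it would match the PP summary.

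**Step 2: how the protocol classes bleeding time.**

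| Place | Role |
|---|---|
| Synopsis outcome variables; 2.2; 4.3; 6.2.3 | Pharmacodynamic |
| Synopsis safety list; 6.2.1 | Not listed as a safety outcome |
| 3.1.1 | Safety result reviewed before multiple dosing |
| 3.1.2, 3.3.5.1 | Part of the escalation-stopping and discontinuation criteria |
| 3.1.3 | Safety result reviewed before discharge |

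It has both roles, but the analysis plan serves only the first.

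**Step 3: direction of the exclusions.** An interacting medicine could lengthen bleeding time. Interrupted dosing would more likely shorten it. Removing such subjects could move the summary either way.

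**Step 4: what the other outputs cover.** Adverse events are listed for all subjects (6.4(e)). Section 6.4(c) does not say which population the bleeding-time listing covers. Change from pre-dose baseline is planned for continuous laboratory data, ECG and vital signs (6.4(f) to (h)) but is not mentioned for bleeding time, although the prolongation criterion gives an increase over baseline as its example. Under 6.2.3.2 a reading above 60 minutes is counted as 60 and the affected statistics are flagged as biased. If that subject is outside the PP set, the planned summary shows neither the value nor the flag.

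**Step 5: scale.** Section 6.5 gives 15 active and 3 placebo subjects per ethnic group-by-dose cell. Section 6.4 combines placebo over the two cohorts, giving 3 + 3 = 6 per ethnic group.

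- One active exclusion: 1/15 = 6.7% of the cell. Three: 3/15 = 20%.
- One placebo exclusion: 1/6 = 16.7%.

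If one subject with value x is excluded and the other 14 average m, the safety-set mean differs from the PP mean by (x − m)/15. The values below are assumed for illustration, with m = 12 minutes:

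| x (min) | (x − 12)/15 | Safety-set mean | PP mean |
|---|---|---|---|
| 9 | −0.2 | 11.8 | 12.0 |
| 15 | +0.2 | 12.2 | 12.0 |
| 30 | +1.2 | 13.2 | 12.0 |
| 60 | +3.2 | 15.2 | 12.0 |

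The difference is small unless the excluded value is extreme. In that case the reported maximum may also fall.

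**The case against.** The strongest reply is that the plan is consistent. Bleeding time is treated as pharmacodynamic throughout and is absent from the safety outcome lists, so the sentence sending safety data to the safety population does not reach it. A reader might infer that the two sentences in 6.3 contradict each other; they do not. This part of the reply stands, and the PP table is the right one for the PD objective.

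A reader might also infer that the PP rule weakens subject protection or hides the worst cases. The documents do not support either reading.

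- The reviews in 3.1.1 to 3.1.3 and 3.3.5.1 use individual results with no PP filter.
- Prolongation alone does not meet the stopping or discontinuation criterion. It must come with moderate to severe bleeding and/or significant laboratory or vital-sign abnormalities, and those are reported in the safety population.
- A long bleeding time is not itself a protocol deviation, so an extreme value caused by the study drug alone stays in the PP set. Only an extreme value that coincides with an excluding deviation is lost from the summary.

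Such coincidences should be uncommon. Subjects are resident from Day −2 to Day 13, dosing is supervised (3.4.6) and other medication is restricted. Section 3.4.5 does allow any medicine needed for a subject's safety and well-being, so they are not excluded.

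Finally, extra tables are often left to the SAP. That would answer a silent protocol, but 6.3 is not silent: it names the set for bleeding time and the single condition under which that set changes.

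**Conclusion.** The point holds as a gap in coverage. Followed exactly, section 6.3 gives no summary of bleeding time in all dosed subjects whenever the PP and safety sets differ, although the protocol relies on the measure in its safety reviews. The PP assignment is legitimate for the PD objective, and no contradiction exists.

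The size cannot be derived from the documents. They give neither an expected distribution of bleeding times nor an expected number of PP exclusions, and the illustrative means rest wholly on assumed values. What can be stated is that one exclusion removes 6.7% of an active cell or 16.7% of an ethnic group's combined placebo subjects, and that the bias could go either way. The conclusion assumes that at least one dosed subject is excluded and that the SAP, which is not shown, does not add the missing summary.

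**What to change.** Amend sections 6.3 and 6.4(c) so that the PP summary of bleeding time remains the PD analysis and a second summary uses the safety population. Preferably the second table should also give change from pre-dose baseline and counts at thresholds the protocol already contains: longer than 12 minutes (3.1.3), longer than 60 minutes (4.3.2) and an increase of more than 30 minutes (the example in 3.1.1, 3.1.2 and 3.3.5.1). These are for tabulation only; no clinical rule changes.

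The cost is one extra table when the sets differ, and no second population table when they are identical. Data collection and sample size are unchanged.
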